6.2.6 Follow-up period and trial completion

The Follow-up Period is 4 weeks and consists of two visits, FUp1 and FUp2, with two intermediate home sampling timepoints. Please see the [Flow Chart](#) for timelines and visit details. No study medication is taken during the Follow-up Period.

The Residual Effect Period (REP) in this study is 7 days, therefore visit FUp1 should be performed no earlier than 7 days after the End of Treatment Visit.

Other follow up visits and assessments should be scheduled relative to the EoT visit i.e., there will be home sampling without visit at 2 weeks and 3 weeks after EoT, and FUp2 should be 4 weeks after EoT.

Patients who prematurely discontinue during the Run-In Period should have FUp1 as a minimum. Patients randomised to the Treatment Period should be encouraged to complete all visits and procedures in the FUp period. If the patient does not wish to complete all visits or procedures, they should have FUp1 as a minimum.

For patients who prematurely discontinue during the Run-In Period, aldosterone samples do not need to be taken at FUp1 or FUp2.

For patients who have not had [REDACTED] collected at EOT, these samples do not need to be taken at FUp1 and/or FUp2.

Participation in this trial is concluded once FUp2 has been completed. Additional visits may be scheduled for continued safety monitoring after the FUp2 visit if needed in the opinion of the investigator. Abnormal assessments or lab values judged clinically relevant by the investigator will be monitored until they return to a medically acceptable level.

7. STATISTICAL METHODS AND DETERMINATION OF SAMPLE SIZE

In this study, the primary endpoint is the change from baseline in log transformed UACR measured in First Morning Void urine after 14 weeks. The purpose of this trial is to demonstrate clinical activity of BI 690517 and to determine the optimal dose for phase III.

The methodology for dose finding employing both multiple comparison procedures and modelling techniques (MCPMod) will be applied to the 3 groups of patients with BI 690517 and placebo. In addition, MCPMod will be used to characterise the BI 690517 dose-response relationship separately in (1) patients on a background medication of placebo, and (2) on background medication of empagliflozin.

Dose effects will be assessed separately on each background therapy because both empagliflozin and BI 690517 have a haemodynamic effect which leads to an acute eGFR decrease. It will be important to assess the effects of both drugs alone, and in combination with a staggered treatment initiation.

7.1 NULL AND ALTERNATIVE HYPOTHESES

For the primary endpoint, the null hypothesis is that the dose-response curve is flat across the 3 BI 690517 doses and the placebo, whereas the alternative hypothesis of a non-flat dose-response curve indicates a clinical benefit of BI 690517 in at least one of the doses. The null hypothesis of a flat dose-response curve across the 3 BI 690517 doses and the placebo will be assessed in the following order: (1) in all patients (regardless of background therapy), (2) in patients on a background medication of placebo, and (3) on background medication of empagliflozin.

The MCPMod procedure allows for simultaneous evaluation of different potential dose response patterns, while protecting the overall probability of Type I error (one-sided α of 5%, which corresponds to two-sided α of 10%). The pre-specified models and their parameters used for this test will be outlined in [section 7.2.3](#).

7.2 PLANNED ANALYSES

7.2.1 General considerations

The following analysis sets will be defined for statistical analyses:

Entered Set (ES): This patient set includes all patients who signed informed consent. The ES will be used for the analysis of patient disposition.

Randomised Set (RS): This patient set includes all entered and randomised patients based on the treatment groups they were randomised to at the randomisation prior to the Treatment Period, regardless of being treated by BI 690517 or not. The RS will be used for the analyses of protocol deviations as well as demographics and baseline characteristics.

Treated Set (TS): This patient set includes all patients who received at least one dose of BI 690517 or matching placebo. The TS is based on actual treatment patients have received and will be used for safety analyses.

Full Analysis Set (FAS): This patient set includes all randomised patients who had at least one baseline measurement of UACR at week 6, 7, or 8 and at least one post-baseline measurement. The FAS will be the main analysis set for the analysis of efficacy.

The pharmacokinetic set (PKS): This patient set includes all patients in the TS who provided at least one PK parameter that was not excluded because of protocol deviations relevant to the statistical evaluation of PK endpoints as defined in [section 5.3](#).

Further analysis sets will be defined in the TSAP, if needed.

7.2.2 Handling of Intercurrent Events

The expected intercurrent events of interest in this trial are restricted to the Treatment Period and are defined as:

- Premature treatment discontinuation of BI 690517
- Down-titration of BI 690517
- Use of SGLT2i as concomitant medication
- Death

The strategies for handling intercurrent events in this trial are summarised in [Table 7.2.2: 1](#).

Table 7.2.2: 1 Summary of strategies for handling intercurrent events

Estimand strategy	Treatment	Intercurrent event handling
Primary	Randomised treatment	
 - BI 690517 discontinuation: include data prior to study medication discontinuation - Down-titration of BI 690517: include data prior to down-titration - Death: include data prior to death - Use of SGLT2i: include all available data
Supplementary 1	Randomised treatment	
 - BI 690517 discontinuation: include all available data - Down-titration of BI 690517: include all available data - Death: include data prior to death - Use of SGLT2i: include all available data

The primary approach will include all data prior to the intercurrent event, so any data collected after the intercurrent event will be excluded from the primary analysis except for the use of SGLT2i as concomitant medication. Patients will be analysed according to their randomised treatment. The analysis period for the primary approach starts from randomisation to the Treatment Period until either intercurrent event or EoT at week 14, whichever comes first. This approach is analogous to a hypothetical approach with respect to BI 690517.

Supplementary 1 approach will include all data collected even after intercurrent event, except for death. Every attempt will be made to follow up with patients who discontinue treatment prematurely until the end of their planned study participation. Patients will be analysed according to their randomised treatment. The analysis period for the supplementary 1 approach starts from randomisation to the Treatment Period until EoT at week 14. This approach is analogous to the treatment policy approach.

Handling of intercurrent events that are not listed will be decided by blinded review based on the general principle outlined and will be documented in the TSAP.

7.2.3 Primary objective analyses

The primary objectives are to demonstrate a non-flat dose response curve, quantify the treatment effect, and evaluate the dose-response relationship. The primary analysis will be performed on the FAS.

For dose finding, multiple comparison procedures and modelling techniques (MCPMod) will be applied. The primary estimand of interest is the treatment effect using the primary approach ([Table 7.2.2: 1](#)).

Treatment effect

The primary analysis will first address a dose-response relationship between doses of BI 690517 and placebo by adopting an MMRM in groups testing the treatment of BI 690517.

Reduction in log transformed UACR from baseline will be used as the response variable in the MMRM.

This model will include fixed effect of treatment at each visit as categorical variable, and fixed effect of log transformed baseline UACR at each visit as continuous variable. Visit will be treated as repeated measure with an unstructured covariance structure for the within-patient variability.

Statistical model (MMRM):

$$y_{ijklm} = \beta_j U_i + \tau_{jkm} + \eta_l + e_{ij},$$

where

$$e_{ij} \sim N(0, \Sigma),$$

y_{ijklm} = reduction in log transformed UACR from baseline for participant i at visit j in stratum l receiving dose level k on background therapy m ,

U_i = the baseline* measurement of log transformed UACR of participant i ,

β_j = coefficient of baseline effect at visit j ,

τ_{jkm} = the effect of dose level k at visit j on background therapy m ,

η_l = the effect of stratum l for having diabetic kidney disease or not,

e_{ij} = the random error associated with the j th visit of the i th participant. Errors are independent between participants,

Σ = an unstructured covariance matrix.

*: baseline is defined as the mean of all non-missing assessments at weeks -2, -1, and 0 prior to the treatment period.

The estimates will be produced for each background therapy separately, and for all patients combined. For the combined analysis, the individual estimates are weighted by the number of patients randomised at the second randomisation. To perform multiple comparison in the MCPMod across doses, predicted average response for each dose group and the standard errors from the MMRM will be used for the MCPMod analysis. The MCPMod analysis will be run for each background therapy and for all patients combined (three times in total).

A non-flat dose-response relationship is established if for the primary endpoint, the null hypothesis of no dose effect (i.e., a flat dose-response curve) is rejected for at least one of the pre-specified dose-response models with respect to the one-sided type I error at 5% after multiple comparisons adjustment.

Dose finding

The second primary objective is to determine the therapeutic dose. The trial will characterise the dose-response curve for BI 690517 by assessing 3 doses and placebo. The response is the change from baseline in log transformed UACR measured in First Morning Void urine after 14 weeks of treatment with BI 690517 or matching placebo. Patients will be evaluated by the dose group they were assigned to at randomisation for primary analysis in the MCPMod analysis.

The analyses for dose-finding will be performed using MCPMod whereby several possible dose response models (patterns) will be evaluated to identify the best-fitting model or subset of models (refer to [Figure 7.5: 1](#)). If efficacy is established, the statistically significant (best fitting) model(s) from the candidate set will be refitted to the data to generate new estimates for all model parameters from the data. The final model will be obtained via model averaging across the significant models based on Akaike Information Criterion (AIC). The target dose(s) can be estimated from that model by incorporating information on the minimum clinically relevant effect and accounting for safety. Doses within the dose range investigated (0 to 20 mg, total daily dose) will be considered.

[figure not shown]

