Eligible patients will be randomised to treatment using a stratification algorithm that helps ensure balance between the treatment groups with respect to prognostic variables such as eGFR and UACR. A target of approximately 30% of patients will be randomised during the run-in period in each of the disease types: diabetic kidney disease and non-diabetic kidney disease. Patients with diabetes may have diabetic kidney disease, non-diabetic CKD aetiologies, or a combination; for the purpose of categorising diabetic status, they will be classified as having diabetic kidney disease.

From the start of the screening until the end of the trial, at various time points patients will collect their First Morning Void urine for UACR analysis. These timepoints are listed in the [FMV and 24-hour Urine Sampling Flow Chart](#). First morning void urine will be collected before the daily dose of study medication. 24-hour urine samples will also be collected prior to the start of the Treatment Period and at EOT. The patient will be equipped with urine collection containers to collect 24-hour urine and First Morning Void urine.

To decrease the burden on patients, where local regulations allow, samples taken at home between visits or when a home visit occurs will be shipped from the patient's home to a central laboratory for analysis. Where this is not possible alternative arrangements will be made, e.g. samples taken to the investigational site. Samples taken directly prior to a physical visit at the site will be taken to the site to be processed by the site staff.

Beyond analysis for safety, urine and blood samples in this trial will serve for biomarker analysis including UACR.

Following the Treatment Period, or at the time trial treatment in the Run-in Period or the Treatment Period is permanently discontinued, patients will have an End of Treatment (EoT) visit. This will be followed by a 4-week follow-up period off-treatment. A first follow-up visit (FUp1) at least 7 days later is considered as the end of the Residual Effect Period (REP).

Until the end of REP all AEs and changes to concomitant medication need to be collected, documented and reported. Patients who discontinue prematurely during the Run-In Period must attend FU_{p1} at least. All other patients should be encouraged to complete the full follow-up period.

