3.2 DISCUSSION OF TRIAL DESIGN, INCLUDING THE CHOICE OF CONTROL GROUP(S)

This trial has been designed to assess efficacy and safety of BI 690517 alone, and in combination with empagliflozin, as likely initiated in clinical practice. It also allows the opportunity to find the optimal dose of BI 690517 to be used for future development, on its own and / or as a fixed dose combination with empagliflozin.

Patients will initially start on 8 weeks of empagliflozin or placebo in the Randomised Run-in Period and will then receive 14 weeks of treatment with BI 690517 or placebo in the Treatment Period in addition to the empagliflozin or placebo treatment. It is important that patients run in on empagliflozin first, before starting treatment with BI 690517, for safety reasons since both drugs have potentially similar haemodynamic effects. 8 weeks of empagliflozin treatment is considered sufficient to reach stable haemodynamic levels, before starting with BI 690517.

A parallel group design was chosen to investigate three different dose regimens of BI 690517 alone and in combination with empagliflozin. The first parallel group will investigate three different dose regimens of BI 690517 and placebo. The second parallel group will

investigate three different dose regimens of BI 690517, in combination with empagliflozin, versus empagliflozin+placebo. Placebo is used to control for observer and subject bias, and randomisation to control for assignment bias.

The study design involves two randomisations. The first run-in randomisation to empagliflozin and placebo is required for two purposes. Firstly, the run-in randomisation will ensure an equally distributed patient population to the empagliflozin and placebo groups followed by second randomisation to treatment groups. Secondly, a staggered approach starting empagliflozin during the run-in period, followed by later initiation of BI 690517 was chosen to enhance patient safety. Both, empagliflozin and BI 690517, have a haemodynamic effect which leads to an acute eGFR decrease. Staggered treatment initiation is planned to reduce such effect.

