7.4 RANDOMISATION

BI will arrange for the creation of the randomisation scheme and the packaging and labelling of trial medication. Patients will be randomised to double-blind treatment. Approximately equal numbers of patients will be randomised to each treatment group. The randomisation list will be generated using a validated system, which involves a pseudo-random number generator so that the resulting randomisation scheme will be both reproducible and non-

predictable. The block size will be documented in the Clinical Trial Report. Access to the codes will be controlled and documented.

In this study, patients will undergo a 2-step randomisation, with the first randomisation performed prior to the Randomised Run-in and the second randomisation performed prior to the Treatment Period. Patients must fulfil the criteria (as described in [section 3.3.2](#)) in order to be randomised into the Treatment Period. In order to ensure a balance of patients between treatment groups, the trial will use stratified randomisation according to prognostic variables eGFR (< 45 and ≥ 45 mL/min/1.73 m²), UACR (≤ 750 and >750 mg/g). At the first step, patients will be randomised to the treatment of empagliflozin or matching placebo in a 1:1 ratio for 8 weeks. At the second step, patients will be randomised to the Treatment Period in a 1:1:1:1 ratio for the treatment of 3 doses of BI 690517 (3 mg QD, 10 mg QD, and 20 mg QD) and matching placebo for 14 weeks, on the top of empagliflozin or matching placebo from the first randomisation.

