4. CHANGES IN THE PLANNED ANALYSIS OF THE STUDY

This section is not applicable as no change has been made.

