6. GENERAL ANALYSIS DEFINITIONS

6.1 TREATMENT(S)

For basic study information on treatment to be administered, assignment of treatment groups, and selection of doses, refer to CTP Sections 3 and 4. This phase II trial will be performed as a double-blind, placebo-controlled and parallel dose group trial to investigate efficacy and safety of multiple doses of oral BI 690517 over 14 weeks, alone and in combination with empagliflozin, in patients with diabetic and non-diabetic chronic kidney disease.

During the Run-in Period, eligible patients will be randomised in a 1:1 ratio to either receive empagliflozin 10 mg once a day (QD) or placebo matching to empagliflozin 10 mg QD in a blinded manner for 8 weeks. During the Treatment Period, patients who received empagliflozin or placebo matching to empagliflozin in the Run-in Period, respectively, will be randomised in a 1:1:1:1 ratio to receive one of three doses of BI 690517 (3 mg QD, 10 mg QD or 20 mg QD) or placebo. The randomisation will be stratified according to prognostic variables eGFR (< 45 and ≥ 45 mL/min/1.73 m²), UACR (≤ 750 and >750 mg/g). Following the 14-week Treatment Period, or at the time trial treatment is permanently discontinued, patients will have an End of Treatment (EoT) visit, which will be the start of a 4-week follow-up period.

Section 1.2 of the CTP: The Residual Effect Period (REP) of BI 690517 is 7 days. This is the period after the last dose with measurable drug levels and/or pharmacodynamic (PD) effects still likely to be present.

Section 7.2.6 of the CTP: Statistical analysis and reporting of AEs will concentrate on treatment-emergent adverse events (TEAEs), i.e. all AEs that occur between start of treatment and end of the REP. AEs that start before first drug intake and deteriorate under treatment will also be considered as ‘treatment-emergent’. AEs will be summarised by the treatment groups to which the patient was randomised, and the treatment at the onset of AE for any drug-related AE. In addition, summary of patients with down titration (dose reduction) due to AE will be provided.

For the analysis of AEs, the following study phases are defined in Table 6.1: 1.

Table 6.1:1 Study phases for analysis of AEs

Study Analysis Phase	Label	Start (inclusive)	• End (exclusive)
Screening	Screening	Date of informed consent	Date/time of first administration of empagliflozin / placebo

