7.4 PRIMARY ENDPOINT(S)

7.4.1 Primary analysis of the primary endpoint(s)

The primary analysis of the primary endpoint will be analysed according to the primary strategy of handling ICEs (see [Section 5.1](#)).

Refer to Section 7.2.2 of the CTP for a description of the statistical analysis for the change from baseline in log transformed FMV UACR measured at 14 weeks of trial treatment.

The adjusted mean change in log transformed FMV UACR from baseline at 14 weeks and its standard error will be obtained from MMRM for the placebo and treatment groups. For the MMRM model, derived UACRs at baseline, visit 8, visit 9, and EoT, which were described in [Section 6.6.2.1](#), will be used.

SAS code for **the MMRM model** will be based on the following structure:

```
PROC MIXED DATA=alldat cl method=reml;

CLASS visit trt subject;

MODEL chg = baseline*visit visit*trt stratum / ddfm=kr s CL;

REPEATED visit / subject= subject type=un r rcorr;

LSMEANS visit*trt /pdiff=all om cl alpha=0.05 slice=visit;

RUN;
```

In the event of model non-convergence, the methods described in [Section 10.1](#) will be attempted (in order) to overcome it.

MCPMod Analysis

For the primary analysis the dose-response relationship will be modelled using following doses: placebo, 3mg, 10mg, and 20mg, in combination with empagliflozin or empagliflozin matching placebo, respectively. The multiple comparison procedure will then be implemented using optimal contrast tests which control the family-wise type I error rate at a one-sided $\alpha = 0.05$. For the MCPMod test, the optimal contrasts of each candidate model are calculated using the R-function optCont.

For the final evaluation, the contrast will be provided using the expected model means from the candidate set and the estimated variance-covariance matrix extracted from the MMRM model.

Once the significance of a dose-response signal is established, the dose-response profile and the target dose can be estimated using a model averaging approach for significant models.

To select a dose estimation model out of the set of significant models, estimates for each dose group will be calculated and will be based on the final dose-response model. The choice of the target dose will be based upon efficacy as well as considering safety and other relevant information.

[figure not shown]
The following displays are planned:

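### The primary MMRM has no eGFR term, although eGFR category is one of the two randomisation stratification factors

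*Protocol*

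**What the plan says.** Protocol 7.4 states that "the trial will use stratified randomisation according to prognostic variables eGFR" and UACR, with cut-points of 45 mL/min/1.73 m² and 750 mg/g. SAP 6.1 repeats this: "The randomisation will be stratified according to prognostic variables eGFR" and UACR, at the same cut-points. Protocol 3.1 describes a "stratification algorithm that helps ensure balance between the treatment groups with respect to prognostic variables such as eGFR and UACR". Diabetic status is not a stratification factor in the current text.

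The primary model in protocol 7.2.3 has three fixed components:

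- log baseline UACR with a visit-specific slope;
- dose by visit by background therapy;
- a term defined as "the effect of stratum l for having diabetic kidney disease or not".

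The SAP 7.4.1 code is "MODEL chg = baseline*visit visit*trt stratum / ddfm=kr s CL", with "CLASS visit trt subject" as its class list. The term `stratum` is not defined in the SAP text available to us. SAP section 4 says of changes to the planned analysis: "This section is not applicable as no change has been made". By contrast, SAP 7.5.2 does adjust the UACR responder logistic regression for the stratification factors.

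**The concern.** A trial that balances its arms on a factor it calls prognostic should normally carry that factor into the primary model. Stratification removes the factor's variation from the comparison between arms. A model without the factor leaves the same variation in the residual, so its standard error overstates the true sampling error of the treatment contrast. Protocol 7.2.3 feeds the MMRM standard errors into MCPMod, so the overstatement reaches both the contrast tests and the confidence bands.

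UACR is already covered by the continuous baseline, so the gap is eGFR alone. What is at stake is some power and slightly wide intervals, not validity.

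**Working it through.** **1. Stratification factors against model terms**

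| Factor | Randomisation (protocol 7.4, SAP 6.1) | Primary MMRM (protocol 7.2.3) |
|---|---|---|
| UACR | yes, cut at 750 mg/g | yes, continuous log baseline by visit |
| eGFR | yes, cut at 45 mL/min/1.73 m² | no |
| Diabetic kidney disease | no | yes, as the stratum term |

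SAP section 4 declares no change, so `stratum` in the SAP code takes the protocol meaning and eGFR is absent there too. A two-level numeric variable gives the same fit in or out of `CLASS`, so leaving it off that list affects clarity only.

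**2. Reproducing the stated power**

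The documents give no SD, so it has to be back-solved. Inputs from protocol 7.5:

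- doses 0, 3, 10 and 20 mg, equal allocation, one-sided 5%;
- Emax reaching 80% of maximum at 10 mg: 10/(10 + ED50) = 0.80, so ED50 = 2.5 mg;
- exponential reaching 15% of maximum at 10 mg: (e^(10/δ) − 1)/(e^(20/δ) − 1) = 0.15, so δ = 5.77;
- linear.

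With optimal contrasts and a normal approximation, the critical value of the maximum contrast statistic is 1.917 (4 million draws). Solving for the SD:

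- 89.7% power, 60 per arm, effects 0/0.10/0.20/0.35: SD = 0.668;
- 83.1% power, 120 per arm, effects 0/0.10/0.16/0.22: SD = 0.658.

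One SD of 0.66 reproduces both stated powers to within about 1 point (90.2% and about 82.7%) and is used below.

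**3. Cost of the omission**

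Let R² be the share of residual variance that eGFR category explains beyond log baseline UACR and diabetic kidney disease. It is an assumption, taken as 1%, 5% and 10%. With full balance on eGFR:

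- the true SD of the contrast is 0.66 × √(1 − R²) under either model;
- the model without eGFR divides by an SE inflated by 1/√(1 − R²), so the effective critical value is 1.917/√(1 − R²).

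| | R² = 1% | R² = 5% | R² = 10% |
|---|---|---|---|
| SE inflation, 1/√(1 − R²) | 1.005 | 1.026 | 1.054 |
| Effective critical value | 1.927 | 1.967 | 2.021 |
| One-sided type I error without eGFR | 4.89% | 4.49% | 3.99% |
| Power, 60 per arm, without → with eGFR | 90.35 → 90.53 | 90.70 → 91.54 | 91.14 → 92.77 |
| Gain in points | 0.17 | 0.84 | 1.63 |
| Power, 120 per arm, without → with eGFR | 82.88 → 83.13 | 83.21 → 84.48 | 83.66 → 86.16 |
| Gain in points | 0.25 | 1.27 | 2.51 |

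Power without eGFR also rises with R² because balance lowers the true sampling error under both models. Over SD 0.658 to 0.668, the gains at R² = 10% are 1.6–1.7 and 2.5–2.6 points.

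**4. Patient-level check**

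This simulated 6,000 trials of 480 patients, analysed by ANCOVA at week 14. Randomisation used blocks of 4 within eGFR × UACR × background. Assumed shares were 45% with low eGFR, 45% above the UACR cut and 70% with diabetic kidney disease. At R² = 10% under the null, for 20 mg versus placebo:

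| | Without eGFR | With eGFR |
|---|---|---|
| Empirical SE | 0.0810 | 0.0809 |
| Model-based SE | 0.0853 | 0.0808 |
| Type I error, combined analysis | 3.95% | 5.07% |

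The mean estimate was about 0 in both. The empirical SEs agree and only the model-based SE is wrong: 0.0853/0.0810 = 1.053, close to the 1.054 in step 3. Power gains at R² = 1/5/10% were 0.2/0.7/1.7 points at 60 per arm and 0.2/1.2/2.9 at 120 per arm (Monte Carlo SE 0.06–0.22).

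**The case against.** The best counter-argument concerns importance. Every figure depends on an R² that no document supplies. Calling eGFR prognostic does not show that it predicts the 14-week change in log UACR once baseline UACR and diabetic kidney disease are in the model. At 1% the effect is negligible. Even at 10% the test is only mildly conservative, in a Phase II trial with a one-sided 5% alpha. All of this stands, and it caps the weight of the point.

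The figures also assume full balance on eGFR in the analysed data. The block size is not given, the FAS requires an on-treatment post-baseline value, and data after discontinuation or down-titration are dropped. Each of these can weaken the balance, so the type I error and SE figures are limiting cases. The patient-level check was a week-14 ANCOVA, not the planned MMRM.

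The protocol defines its stratum term where it is used, and the SAP assumes familiarity with the protocol, so the labelling is a matter of clarity. SAP sections 10.1 and 10.2 and the protocol's sensitivity section are not in the text available. A definition of `stratum`, or an eGFR-adjusted sensitivity analysis, may be there. Neither would put eGFR into the primary model of protocol 7.2.3.

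The eGFR adjustment that SAP 7.5.2 implies for the responder analysis does not repair the primary model. It shows that the sponsor accepts adjustment for the stratification factors, and no reason is given for treating the primary analysis differently.

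**Conclusion.** The point holds. The primary model leaves out eGFR category, one of the two factors on which patients are randomised. That is certain for the protocol model, and it follows for the SAP model from the declaration of no change. The consequence is limited to overstated standard errors, a conservative dose-response test and wide confidence bands. Its size runs from negligible at R² = 1% to 1.6 (60 per arm) and 2.5 (120 per arm) power points at R² = 10%, given an SD of about 0.66 and full balance on eGFR. The change should be made because it costs almost nothing and aligns the analysis with the randomisation, not because the conclusions are at risk without it.

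**What to change.** - In protocol 7.2.3 and SAP 7.4.1, add the eGFR randomisation category (<45 / ≥45, as recorded for the second randomisation) as a fixed effect and list it in `CLASS`. If the sponsor prefers to omit it, give the reason.
- State which visit's eGFR sets the category. Protocol 7.4 does not say. Protocol 3.2 notes that both drugs "have a haemodynamic effect which leads to an acute eGFR decrease", so a patient's category may differ between the two randomisations.
- Keep log baseline UACR by visit as it is.
- For clarity, keep diabetic kidney disease as a covariate under its own name and define it in the SAP. Correct the SAP 7.4.1 cross-reference, which points to protocol 7.2.2 (intercurrent events) although the model is in 7.2.3.

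The cost is one extra fixed-effect parameter with about 480 patients and a few lines of text and code. No new data are needed.
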